#### 14.2.2 SECONDARY EFFECTIVENESS OUTCOMES

**For R33 Aim 1**, we will evaluate the **effectiveness** the Partners4Pain and Keys to Wellbeing interventions using self-report surveys at 2, 4 and 6 months, measuring secondary outcomes.

Secondary outcome measures include a range of measures consistent with the Biopsychosocial Model of Pain and are recommended common data elements from the HEAL initiatives core pain domains; in addition, we have included important PROMIS based measures with demonstrated reliability and validity in chronic pain populations.

- Pain impact and frequency over the past 3 months measured using the Graded Chronic Pain Scale-Revised (GCPs-R).
- Physical function using the PROMIS 6-item short form v2.0 which measures difficulty doing household activities and agreement with statements on health limitations in physical activities on a 1 to 5 scale.
- Sleep disturbance and duration using the PROMIS 6-item short form v1.0 which measures sleep quality on a 1 to 5 scale from very poor to very good in addition to agreement with statements on sleep quality on a 1 to 5 scale. The average amount of sleep per night in the past month will also be obtained.
- Participation in social roles and activities using the PROMIS 4-item short form v2.0 which measures frequency of trouble doing activities for leisure, work, or with family or friends on a 1 to 5 scale.
- Anxiety will be measured using the Generalized Anxiety Disorder-2 survey (GAD-2) which includes 2 questions that are summed for a total score that can range from 0 to 6.
- Depression will be measured using the Patient Health Questionnaire-2 (PHQ-2) which includes 2 questions that are summed for a total score that can range from 0 to 6.
- Substance use will be assessed using the Tobacco, Alcohol, Prescription medications, and other Substance (TAPS) survey. The TAPS is comprised of an initial 4-item screen for substance use that may lead to further assessment with substance specific surveys when indicated based on the initial 4-item screen.
- Pain catastrophizing will be assessed using the 6-item short form of the Pain Catastrophizing Scale.
- Self-efficacy for managing chronic conditions will be assessed using the PROMIS 4-item short forms for 1) managing daily activities; 2) managing symptoms; 3) managing emotions; and 4) managing social interactions.
- Interoceptive Awareness will be measured using the Multidimensional Assessment of Interoceptive Awareness survey instrument (V2) using the 1) noticing; 2) attention regulation; 3) emotional awareness; and 4) self-regulation subscales.
- Satisfaction with various domains of life (e.g., education, work, family life) will be assessed using the PROMIS 13-item domain specific life satisfaction measure.
- Self-reported use of CIH self-management strategies, medications (over-the-counter and prescription medications - including opioids), and health care (MRIs, injections, hospitalizations, surgeries, provider visits) for back or neck pain will be measured.
- Participants will be asked to report potential side effects by choosing from a list generated from previous studies of pain self-management programs and known potential risks of exercise and mindfulness interventions (R33AT009110, NH170001, R34AT011209).

- Satisfaction with the interventions will be assessed using a question that has participants rate their overall satisfaction ranging from completely satisfied to completely dissatisfied.
- Overall improvement will be assessed with the Patient Global Impression of Change (PGIC) which has participants rate their overall change from very much worse to very much improved.

**For R33 Aim 2**, we will evaluate the ***impact of health disparity related factors on the effectiveness*** of Partners4Pain intervention for primary and secondary outcomes described above through subgroup analyses which account for the potential relationships and complexities between disparity factors. See Section 15.4.2.

#### 14.2.3 IMPLEMENTATION & DISPARITY MITIGATING OUTCOMES

**For R33 Aim 3**, we will assess and describe ***views of factors that could facilitate implementation and mitigate disparities*** to prepare for the long-term translation of the intervention to community partner organizations within and beyond the trial. We will use mixed methods quality improvement data collection of Study Participant and Community Stakeholder views and relevant flow data.

Study Participants will be asked to complete mixed methods surveys collected querying:

- Views on barriers/facilitators to reach and participation
- Perceived effectiveness of the interventions
- Their satisfaction with and use of specific program activities
- The extent to which they felt the program met their capability, opportunity, and motivational (COM) needs
- Their views of the intervention's overall affordability, practicality, effectiveness, acceptability, safety, and equity (APEASE, which is part of the COM model)
- The ability of the study team to create a supportive environment and develop relational alliances that fostered norms of inclusion and cultural sensitivity. This includes a measure detailing perceived discrimination in healthcare that will be adapted to assess perceived discrimination within the study.

Community Stakeholders will also participate in a mixed methods evaluation (e.g., via interviews, focus groups, field notes) of their views of the intervention's APEASE features, the nature and quality of the researcher-community partnership, and other domains that emerge as important for sustainability and translation.

Flow data related to the implementation and disparity mitigating outcomes include:

- Number, proportion, and representative characteristics of Study Participants; reasons for participation or not by social determinants of health factors
- Number, proportion, and representative characteristics of Community Partner Organizations; reasons for participation
- Number, proportion, and representative characteristics of Community Facilitators; reasons for participation

#### 15 STATISTICAL CONSIDERATIONS

## 15.1 HYPOTHESES

**Phase I (R61):** No hypotheses have been formulated for the R61 phase of the project given the focus on quality improvement and feasibility.

**Phase II (R33):**

Aim 1 Hypothesis: The Partners4Pain program will be more effective in reducing the primary outcome of pain intensity and interference, in addition to secondary outcomes relative to the Keys to Wellbeing program (active control).

Aim 2 Hypothesis: Through sub-group analyses accounting for complex relationships between disparity factors and multi-level evaluation of community stakeholders, we will gain insights into the program's ability to mitigate disparities (e.g., by overcoming capability, opportunity, and motivational (COM) barriers, as well as obstacles related to affordability, practicality, effectiveness, acceptability, safety, and equity (APEASE)).

## 15.2 SAMPLE SIZE

### 15.2.1 R61 RANDOMIZED PILOT STUDY

A total of 30 to 60 individuals will be enrolled in the R61 Randomized Pilot Study. The sample size has been informed by previous pilot studies by the investigators who have found approximately 15-20 individuals per group sufficient for informing the feasibility of larger, randomized clinical trials. We anticipate needing to consent approximately 60 to 80 participants to enroll 30 to 60 individuals into the trial.

### 15.2.2 R33 RANDOMIZED HYBRID EFFECTIVENESS-IMPLEMENTATION TRIAL

Our sample size for the R33 Randomized Hybrid Effectiveness-Implementation Trial is based on findings from the literature on the PEG instrument (our primary outcome measure), including data on responsiveness and variability. We want at least 80% power to detect a group difference of approximately one unit or 10 percentage points on the PEG (0-10 scale) based on the mean of the 2, 4, and 6 month measures. We conducted simulation studies mimicking the structure of our planned study to assess the impact of sample size and group treatment factors (class size and number of classes) on power and detectable group difference. We used data on back pain intensity from the active control intervention (Keys to Wellbeing) in our team's recent trial of physical activity in older adults (R33AT00911) to inform intra-class correlation. We generated normally distributed longitudinal measurements from the 0-10 PEG scale with a moderate intra-individual correlation of 0.25, an intra-class correlation of 0.05, and a residual standard error of 2.5 units. The mean response was a function of normally distributed individual- and class-level random effects (with variances chosen to achieve the above correlations) as well as a constant fixed effect of treatment at the 2-, 4-, and 6-month time points. The mean PEG during follow-up was compared between treatment groups using a linear mixed model with fixed effects for treatment and baseline PEG and random effects for individual and class. We carried out simulations across a number of scenarios with class sizes ranging from 10 to 16 participants and a total sample size of 300. In all scenarios, our planned sample size yielded greater than

80% power for a treatment effect of approximately 0.9 units (0-10 scale), corresponding to a standardized between group effect size (mean difference/SD) of 0.36, which we regard as a clinically meaningful difference for pain intensity and interference, and is consistent with recommendations in the literature. To account for up to 20% loss to follow up, we plan to enroll a total of 376 participants.

### 15.3 POPULATIONS FOR ANALYSES & GENERAL APPROACH (R33)

The primary analysis for the R33 Randomized Hybrid Effectiveness-Implementation Trial will use an intent-to-treat (ITT) approach with all enrolled subjects included in the analysis. Per-protocol analysis including only participants compliant with study protocols will be conducted as a secondary analysis. Secondary analyses are exploratory and will not be corrected for multiple comparisons. We will use hierarchical linear mixed model regression analyses to account for repeated measures within trial participants (the unit of randomization) in addition to the clustering of individuals within classes when receiving the experimental or control interventions. Missing data analyses will be informed by the pattern and reasons for missing data and will include multiple imputation (data missing at random) and sensitivity analyses using pattern mixture models (data not missing at random), if appropriate. This approach has been applied in previous trials by the investigators and highlighted as an exemplar in Annals of Internal Medicine.

### 15.4 DATA ANALYSES

#### 15.4.1 R61 PHASE

**Aims 1 & 2:** Mixed method assessment will be conducted. Quantitative data will be analyzed using descriptive statistics when appropriate. For the qualitative analysis, experienced members of the study team will apply rapid deductive, directed content analytic methods of individual and group interviews in real-time, audio-recordings of interviews, and text from open-ended surveys. The coding structure and operational definitions will be guided by the study's conceptual models to provide insights into barriers and facilitators to future implementation. Directed content analyses will also allow for inductive gathering of important themes that might fall outside of our chosen models and frameworks. Rapid approaches have been advocated for implementation research as they balance rigor with efficiency, yielding timely and meaningful evaluation of stakeholder needs and perspectives that can be more quickly matched to solutions. This is in contrast to traditional qualitative methods which rely on resource-heavy methods including transcribing interviews verbatim and in-depth coding of transcripts which take more time. Given the short time frame between the R61 and future R33 study, a rapid analytic approach is most appropriate.

In addition to using rapid qualitative approaches, we may also apply traditional qualitative methods when more nuanced information would be helpful. In these instances, we will use semi-structured interview guides for individual stakeholder interviews and focus groups which will be recorded and transcribed verbatim. Teams of 2-3 will perform in-depth, directed content analyses of the transcripts applying a codebook in NVivo qualitative software. We will use deductive approaches aligned with the study's models and frameworks, as well as inductive thematic coding to document other important information that falls outside the coding structure. Representative quotations will be identified; when

useful (e.g., to gain insight as to theme importance) we will also quantify themes by categorizing them as present or absent for each case, and presented descriptively as frequencies.

**Aim 3:** Mixed method analyses will be conducted. Quantitative data will be presented using descriptive statistics (e.g. means, percentages). No between group statistical comparisons are planned for the R61 Randomized Pilot Study due to the small sample size and focus on feasibility. Qualitative data will be analyzed using the methods described above for Aims 1 and 2.

#### 15.4.2 R33 RANDOMIZED HYBRID EFFECTIVENESS-IMPLEMENTATION TRIAL

##### Primary Analysis

For the primary analysis, we will use mean PEG during follow-up (at 2, 4, and 6 months) as the outcome. The effect of treatment will be assessed using a hierarchical linear mixed model with fixed effects for treatment and baseline PEG and random effects for individual and class. In addition, we will test for evidence of an interaction between time and treatment by fitting a mixed model with an interaction between the treatment group indicator and follow-up time (viewed as a categorical random variable) and using a likelihood ratio test to assess whether the interaction terms are jointly significant. The results of this analysis will inform the interpretation of the primary analysis and guide secondary analyses. Analyses will be carried out using the statistical software R.

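### The R33 primary model has no visit term, so when visits are missing its single treatment coefficient can drift slightly from the equal mean of months 2, 4 and 6; the drift costs almost nothing to remove

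*Combined protocol and SAP*

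**What the plan says.** Section 15.4.2 (Primary Analysis) states "we will use mean PEG during follow-up (at 2, 4, and 6 months) as the outcome" and assesses treatment with a "hierarchical linear mixed model with fixed effects for treatment and baseline PEG and random effects for individual and class". Follow-up time is not among the fixed effects. It enters only in a separate model that tests treatment by categorical time, whose result is to inform interpretation, and in the secondary longitudinal analyses.

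No section says outright whether a record is a person or a visit, but two point to visits:

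- Section 15.3: "We will use hierarchical linear mixed model regression analyses to account for repeated measures within trial participants".
- Section 15.2.2 generated longitudinal PEG measurements with "a constant fixed effect of treatment at the 2-, 4-, and 6-month time points", then analysed them with the same terms: "The mean PEG during follow-up was compared between treatment groups using a linear mixed model with fixed effects for treatment and baseline PEG".

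Section 15.2.2 also sets the target that the trial is powered on, a between-group difference in the average of the three follow-up visits. Section 15.3 plans multiple imputation and, if appropriate, pattern-mixture sensitivity analyses. It does not say whether imputation feeds the primary estimate.

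**The concern.** This is the trial's one confirmatory comparison, and its target is an average over three fixed visits. A model on visit records with one treatment coefficient and no visit term estimates that average only if the visits are balanced. Two separate things can go wrong when they are not.

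1. **Shared time trend.** If PEG falls during follow-up in both arms and one arm supplies fewer late visits, that arm's records come disproportionately from the earlier, higher-PEG period. Part of the time trend then passes into the treatment coefficient. The benefit is understated if the experimental arm loses more and overstated if the control arm does.
2. **Changing effect.** If the effect differs by visit, the coefficient weights visits by the data available, so missing late visits pull it toward the early effect. This happens even when loss is equal in the two arms.

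Both conditions are plausible here. Up to 20% loss is planned for. Month 2 is counted from the start of the groups, with a window opening 21 days early (Table 6), so at about day 61 − 21 = 40. The ninth weekly session falls 8 weeks after the first, at about day 56. Some month 2 assessments may therefore precede the end of the programme. The power simulation assumed a constant effect, so it could not show the second problem.

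**Working it through.** **Inputs from section 15.2.2.** SD 2.5; within-person correlation 0.25; class correlation 0.05; effect 0.9; 300 analysed; class size 10 to 16; loss up to 20%; 376 enrolled. Two-sided alpha 0.05 is assumed, because the documents do not state it.

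**The plan's own figures.** 300/0.8 = 375, against 376 stated. Since 0.9/2.5 = 0.36 matches the stated standardized effect, 2.5 is taken as the total SD and the variance is 6.25. Class variance is 0.05 × 6.25 = 0.3125, person variance 0.25 × 6.25 − 0.3125 = 1.25, and residual variance 4.6875. With m per class:

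SE = √{2 × [(1.25 + 4.6875/3)/150 + 0.3125 × m/150]}

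This gives 0.281 for m = 10 and 0.323 for m = 16, so power for 0.9 is 89% and 80%. The power statement is reproduced.

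**If the record were one mean per person.** The person effect and the residual would be the same quantity. On simulated data the log-likelihood was identical (−313.76) for every split between them, and in R lme4 refused the fit. nlme returned an arbitrary split, but its treatment estimate and SE (−1.043, 0.328) equalled those of the class-only model.

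**Visit records, no visit term.** Loss is taken as monotone and unrelated to PEG, and class is left out of the weights. A person with n visits has weight w(n) = 1/(1.25 + 4.6875/n), so w(1) = 0.1684, w(2) = 0.2783 and w(3) = 0.3556. If PEG falls linearly by d from month 2 to month 6, the average shift in a person's records is 0 (n = 1), −d/4 (n = 2) or −d/2 (n = 3). An arm's expected shift is the w-weighted mean of these, and the bias is the difference between arms.

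All loss at month 6:

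- 15% lost: (0.85 × 0.3556 × 0.5 + 0.15 × 0.2783 × 0.25)/(0.85 × 0.3556 + 0.15 × 0.2783) = 0.4697, a shift of −0.4697d.
- 25% lost: the same formula gives 0.4483. Bias at 15% v 25% = 0.0214d.
- 10% lost gives 0.4800 and 30% gives 0.4372. Bias at 10% v 30% = 0.0428d.

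Half of each arm's loss before month 4: 0.4656 − 0.4404 = 0.0252d at 15% v 25%, and 0.4775 − 0.4270 = 0.0505d at 10% v 30%.

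| Loss by month 6 | Timing of loss | d = 0.8 | d = 1.5 |
|---|---|---|---|
| equal in both arms | either | 0 | 0 |
| 15% v 25% | all at month 6 | 0.017 | 0.032 |
| 15% v 25% | half before month 4 | 0.020 | 0.038 |
| 10% v 30% | all at month 6 | 0.034 | 0.064 |
| 10% v 30% | half before month 4 | 0.040 | 0.076 |

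If three quarters of the fall occurs by month 4 (shifts −0.375d for n = 2 and −0.583d for n = 3), the all-at-month-6 rows become 0.014 to 0.027 and 0.029 to 0.053. With a categorical visit term the expected bias was 0.000 in every scenario tried.

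**Effect that grows, equal 20% loss.** Take effects of 0.5, 0.9 and 1.3, whose equal mean is 0.90. People with three, two and one visits carry mean effects of 0.9, 0.7 and 0.5.

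- All loss at month 6: (0.8 × 0.3556 × 0.9 + 0.2 × 0.2783 × 0.7)/(0.8 × 0.3556 + 0.2 × 0.2783) = 0.867.
- Half before month 4: 0.863.

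The shortfall is 0.033 to 0.037. A visit main effect alone leaves it unchanged (0.863); only treatment-by-visit terms averaged with equal weights restore 0.90.

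**Scale.** A bias of 0.05 moves two-sided type I error from 5% to about 5.3–5.4%, and a bias of 0.10 to about 6.1–6.5%.

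**The case against.** A reader might infer that the primary model cannot be fitted, because the section calls the mean the outcome and also adds a person effect. The documents do not support that. Sections 15.2.2 and 15.3 describe repeated measurements within participants, on which the person effect is meaningful. The section never describes averaging each person's available visits, so the worry that one visit would count as much as three has no footing either. Even with one mean per person, only the variance split is undetermined, not the treatment estimate or its SE.

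A reader might also infer that the estimate is biased in general, or by as much as 0.14 of 0.90. It is not biased in general: there is no bias with complete data, or with equal loss and a constant effect. A shift near 0.14 needs loss of about 30–35% in one arm against 5–10% in the other, a time trend and a growing effect all together. The comparator is matched on time, attention and format, and payments are the same for all participants, so nothing in the documents predicts so large a gap.

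The strongest defence is the planned safeguards. Imputing missing visits with visit in the imputation model would complete the data and remove the problem, but section 15.3 does not commit the primary estimate to imputation. The interaction test and the visit-specific analyses would reveal a changing effect, but they leave the primary coefficient as it is.

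**Conclusion.** The point holds as a small, avoidable weakness in the primary model. On visit records, leaving out visit biases the treatment estimate when PEG changes over follow-up and the loss pattern differs by arm. Separately, the single coefficient departs from the equal mean of months 2, 4 and 6 when the effect varies by visit and visits are missing.

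For a constant effect of 0.90 and a PEG fall of 0.8 to 1.5 points, the bias is about 0.01 to 0.03 at 15% v 25% loss and 0.03 to 0.06 at 10% v 30% when loss comes at month 6. The upper ends reach about 0.04 and 0.08 if half of it comes before month 4. Equal 20% loss with the growing effect tried gives about 0.03 to 0.04. All of these are small against an SE of about 0.28 to 0.32. They rest on an assumed time trend, effect pattern and loss by arm, none of which the documents give. The sample size is not affected.

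**What to change.** In section 15.4.2:

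- State that the primary model uses visit-level PEG at months 2, 4 and 6.
- Use fixed effects for treatment, categorical visit, treatment-by-visit and baseline PEG, and keep the person and class random effects. Baseline-by-visit is optional.
- Define the primary effect as the equally weighted average of the three visit-specific treatment differences.
- Take the planned interaction test from this same model.

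The cost is wording and a few model terms, with no extra data or participants. With complete data, adding visit left the treatment estimate and SE unchanged (−1.043, 0.328). With 20% loss, half of it before month 4, the variance per person of an arm's average (before class) rises from 3.04 to 3.06 under the variances above. Since √(3.06/3.04) is about 1.003, the SE grows by less than 0.5%.

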### 9.2 INCLUSION CRITERIA

The following inclusion criteria apply to the R61 Randomized Pilot Study and the R33 Randomized Hybrid Effectiveness-Implementation Trial.

1. Provide a signed and dated informed consent form
2. State willingness to comply with all study procedures outlined in the consent form
3. Be 18 years of age or older
4. Have self-reported chronic back pain (defined as pain in the low or mid back, or neck pain) which has lasted for 3 months or longer
5. Have a score of 3 or higher on the self-reported Pain, Enjoyment of Life and General Activity (PEG) scale (0 to 10)
6. Be a member of one or more of the following NIH-designated health disparity populations:\*
  - a. American Indian/Alaska Native
  - b. Asian
  - c. Black/African American
  - d. Hispanic/Latino
  - e. Native Hawaiian/Pacific Islanders
  - f. Socioeconomically disadvantaged (annual household income less than \$50,000)

\*This project focuses on back pain in populations that experience health disparities (BP-PEHD). These populations are underrepresented in research studies, have less access to resources for the management of back pain, and have poorer outcomes (see Section 5, Introduction). The study is offered in English, but supplementary materials are available in Spanish for individuals where English is a second language. Supplementary materials may also be offered in other languages.

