### 13.1 SCHEDULE OF ASSESSMENTS

Table 6 details the schedule of assessments for Study Participants in the R61 Randomized Pilot Study and the R33 Randomized Hybrid Effectiveness-Implementation Trial.

*Table 6. Schedule of Assessments for Study Participants\*\* (R61 Randomized Pilot Study and R33 Randomized Trial)*

	Initial Screen	BL1	BL2	Intervention Sessions 1-9	Month 2 (-21 to +28 days)	R33 Only	
						Month 4 (-21 to +28 days)	Month 6 (-21 to +28 days)
Flow Data for Feasibility Outcomes+							
Feasibility of recruitment, enrollment, intervention, and data collection rates	X	X	X	X	X		
Baseline Assessments							
PhenX toolkit: Demographics & Core SDH Measures	X	X	X				
Informed Consent	X	X	X				
Inclusion/Exclusion Criteria	X	X	X				
Randomization			X				
Intervention Assessments							
Intervention Attendance, Session Activities, Intervention Administration Form				X			
Effectiveness Measures*							
Pain intensity		X	X		X	X	X
Pain interference		X	X		X	X	X
Pain impact and frequency		X	X		X		X
Self-efficacy for managing chronic conditions			X		X	X	X
Domain specific life satisfaction			X		X	X	X
Physical functioning			X		X	X	X
Pain catastrophizing			X		X		X
Interoceptive awareness			X		X	X	X
Satisfaction/Improvement					X	X	X
Medication use (including opioids)		X			X	X	X
Participation in social roles		X			X		X
CIH self-management use		X			X	X	X
Healthcare use		X			X	X	X
Sleep disturbance/duration		X			X		X
Depression		X			X		X
Anxiety			X		X		X
Substance use		X			X		X
Implementation and Disparity Mitigating Measures (guided by RE-AIM, COM, ConNECT)							
Views and opinions related to barriers, facilitators to interventions and study participation (see Table 9, Study Participants for details)	X	X	X		X		
Satisfaction with and use of specific program activities					X	X	X
COM Assessment Survey					X		

	Initial Screen	BL1	BL2	Intervention Sessions 1-9	Month 2 (-21 to +28 days)	R33 Only	
						Month 4 (-21 to +28 days)	Month 6 (-21 to +28 days)
Supportive Environmental and Relational Alliance Survey					X		
Other Measures							
Adverse events/side effects				X	X	X	X
Study Completion Form					X (R61)		X (R33)
**Schedule of quality improvement data collection activities can be found in Table 9							
*Effectiveness measures collected in R61 for purpose of assessing data collection feasibility only							

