### 13.2.3 BASELINE TWO SCREEN

A second baseline assessment will take place up to 90 days after BL1. This evaluation may be conducted in-person, via videoconference, or by phone and will include the following activities:

- Trained study staff will confirm consent for participation (See Section 16.1)

- Participants will complete a brief self-report web-based survey to confirm eligibility for exclusion criteria that may have developed after the BL1 evaluation (e.g., pregnancy, cancer treatment)
- Participants will complete baseline assessment for self-reported outcome measures listed in Table 6 (see Section 14.2 for detail on individual measures) and the PhenX toolkit measure for discrimination in healthcare.
- Eligible participants will be enrolled in the study and randomized to either the Partners4Pain or Keys to Wellbeing intervention program.

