##### Secondary Analyses

**Responder Analyses:** We will derive responder categories for our primary outcome of pain intensity and interference (PEG) at 2, 4, and 6 months corresponding to reductions from baseline of 30% (minimal improvement), 50% (moderate improvement), 75% and 100% (substantial improvement). Then, we will fit proportional odds models to assess the effect of treatment on the probability of falling into each of these categories. In addition, we will conduct cumulative responder analyses to assess the proportion of responders for all possible levels of pain intensity and interference reduction (0 to 100% reduction).

**Secondary Outcomes:** Secondary numerical outcome measures (e.g., self-efficacy, life satisfaction, physical functioning) will be analyzed similarly to the primary PEG outcome. Generalized linear mixed models will be used for binary and count outcomes.

**Longitudinal Analyses:** Systematic reviews and meta-analyses of interventions for chronic pain and chronic back pain commonly use short-, medium-, and long-term treatment effects for analysis. Therefore, in addition to the analyses of primary and secondary outcomes which provide a measure of cumulative burden over the six-month study period, we will conduct longitudinal analyses with time coded as a categorical variable to quantify group differences in primary and secondary outcomes at 2, 4, and 6 months. Differences in numerical outcomes will be assessed using linear mixed models as described above. Differences in categorical outcomes (e.g., Graded Chronic Pain Scale, health care use) will be assessed using multi-level mixed effects generalized linear models.

**Effect Heterogeneity Analyses:** While it remains important to estimate the overall (mean) effect of an intervention, analyses of intervention studies have increasingly focused on characterizing how population subgroups experience differential treatment effects. Here, we will employ modern statistical machine learning methods (including some co-developed by co-I [name]) to describe how disparity factors (i.e. race, ethnicity, income, wealth, education, health care access) interact to influence how responsive individuals are to treatment. These flexible methods combining matching techniques

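### PEG is scheduled at two visits before randomisation, but the plan names neither as baseline; adjusting for both readings would give the primary contrast a small, free gain in precision

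*Combined protocol and SAP*

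**What the plan says.** All references are to the combined protocol and SAP, R33 phase.

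- **Two readings.** In Table 6 (13.1) the rows "Pain intensity" and pain interference are ticked at BL1 and BL2, not at the initial screen. Section 14.2.1 identifies these domains with the three-item PEG. Sections 13.2.2 and 13.2.3 have participants complete outcome measures at each visit. BL2 may be up to 90 days after BL1, and sessions start within 28 days of randomisation (13.3).
- **One unnamed baseline.** The primary model (15.4.2) is a "hierarchical linear mixed model with fixed effects for treatment and baseline PEG", with random effects for individual and class. The power simulation in 15.2.2 has the same single term. The responder categories in 15.4.2 are described as "corresponding to reductions from baseline of 30% (minimal improvement), 50% (moderate improvement"), then 75% and 100%. None of these places names a visit.
- **Entry threshold.** Section 9.2 requires a PEG score of 3 or more without naming a visit. BL1 assesses eligibility (13.2.2). The BL2 survey is there to "confirm eligibility for exclusion criteria that may have developed after the BL1 evaluation". Table 6, however, ticks inclusion and exclusion criteria at the initial screen, BL1 and BL2.

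**The concern.** A baseline covariate removes outcome variance in proportion to how well it predicts follow-up. Two readings of a variable score predict better than one, and both will already have been collected before allocation. Using only one would leave precision unused, and leaving the term undefined keeps open a choice that could be made after outcomes are seen.

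The responder analysis raises a second issue. If a reading is both the entry test and the denominator of a percentage reduction, people admitted on a chance high score will tend to score lower later whatever the treatment. That would affect the published response percentages. It would also affect the planned comparison in 15.4.2 with studies in populations with low health disparities.

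**Working it through.** **1. The plan's own figures.** Section 15.2.2 gives 300 analysed, intra-individual correlation 0.25, class correlation 0.05, classes of 10 to 16, and an effect of about 0.9 units described as a "standardized between group effect size (mean difference/SD) of 0.36". I assume 1:1 allocation, two-sided 5% and a normal reference, because the plan states none of these.

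- Enrolment: 300 / 0.80 = 375, against 376 planned.
- SD: 0.9 / 0.36 = 2.5, so total variance is 6.25.
- Class variance C = 0.05 × 6.25 = 0.3125. Person variance P = 0.25 × 6.25 = 1.5625. Residual E = 6.25 − 0.3125 − 1.5625 = 4.375.

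With b baseline readings, three follow-ups, 150 per arm and class size m:

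Var(difference) = (2/150) × [P(1 − P/(P + E/b)) + E/3 + mC]

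- One reading: 1.5625 × (1 − 1.5625/5.9375) + 4.375/3 = 1.1513 + 1.4583 = 2.6096.
- Both readings: 1.5625 × (1 − 1.5625/3.75) + 4.375/3 = 0.9115 + 1.4583 = 2.3698.

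| Class size | mC | SE, one | Power, one | SE, both | Power, both | Variance ratio |
|---|---|---|---|---|---|---|
| 10 | 3.125 | 0.277 | 0.902 | 0.271 | 0.914 | 0.958 |
| 13 | 4.0625 | 0.298 | 0.855 | 0.293 | 0.867 | 0.964 |
| 16 | 5.000 | 0.319 | 0.807 | 0.314 | 0.819 | 0.968 |

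The stated power above 80% in every scenario reproduces with one reading. Two readings of the inputs would lower the level of power. A t reference on class degrees of freedom gives 0.758 with one reading and 0.771 with both at class size 16. Taking 2.5 as the residual SD gives about 0.66–0.81 with one reading. The 0.36 effect size supports the total-SD reading, and the gain from the second baseline is of similar size in each case.

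**2. Range of the gain.**
- If 0.25 includes the class component (P = 1.25, E = 4.6875), the variance ratios are 0.970–0.977 for classes of 10–16.
- If the PEG threshold is applied at BL1 (assumed unselected mean 4.5–5.5, SD 2.5), the saving is 2.8–3.7% against BL1 alone and 1.6–2.5% against BL2 alone. A gain remains if the threshold is applied at both visits.
- If the correlation is higher (assumption), class size 13 gives ratios of 0.921 at 0.5 and 0.913 at 0.6. Across class sizes and with selection, the saving is about 5–10%.

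**3. Bias of the primary contrast.** Whole trials were simulated with entry on BL1, classes of 15 and a true effect of −0.90.

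| Correlation | Covariate | Mean estimate | SD of estimates |
|---|---|---|---|
| 0.25 | BL1 | −0.892 | 0.311 |
| 0.25 | BL2 | −0.904 | 0.311 |
| 0.25 | Mean of both | −0.887 | 0.312 |
| 0.5 | BL1 | −0.903 | 0.308 |
| 0.5 | BL2 | −0.906 | 0.306 |
| 0.5 | Mean of both | −0.898 | 0.299 |

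All three are unbiased to simulation accuracy. At 0.25 the gain is too small for this simulation to show. At 0.5 the SE falls by about 3%.

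**4. Responder rates, if entry is judged at BL1 only.** Assumptions: unselected mean 4.5–6.0, SD 2.5, correlation 0.25, scores limited to 0–10, no true change.

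| Responder baseline | Excess over later mean | 30% response with no effect |
|---|---|---|
| BL1 | 0.4–0.8 units | 27–37% |
| BL2 | 0 | 24–30% |
| Mean of both | 0.2–0.4 units | 24–32% |

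BL1 adds about 3 points over BL2 at the high end of the assumed means and about 7 at the low end. Both arms shift together.

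**The case against.** The strongest reply is that this is a clarification and not a flaw. The term baseline PEG is compatible with an average of both readings, so the plan does not say that a reading is dropped. The gain at the plan's inputs is about one power point on a design that already meets its target. BL2, the reading closest to randomisation, is a defensible single baseline. The two-reading mean also only halves the regression to the mean that BL1 carries. All of this stands, and it limits the size of the point. It does not remove it, because both scores are already scheduled and adjusting for both is more precise than either one alone.

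A reader might also infer more than the documents support:

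- **A loss worth about 9% of the sample.** Ignoring classes, one reading explains 0.0625/0.5 = 12.5% of the variance of the follow-up mean, and two explain 0.0625/(0.625 × 0.5) = 20%. The ratio is 0.80/0.875 = 0.914, which suggests some 35 of 376 participants. But the plan's model has a class random effect, and the second baseline cannot reduce that part of the variance.
- **A BL1 baseline dilutes the responder contrast.** With a 0.9-unit effect, the arm difference in 30% response is 12.5–13.9 points with BL1 and 11.7–12.9 with BL2. At correlation 0.25 the odds ratios are 1.76–1.77 and 1.74–1.75. Only at an assumed 0.6 is the BL1 odds ratio slightly lower (2.07–2.11 against 2.12–2.15).
- **BL2 is free of selection, so percentages against it can be undefined.** Up to about 3% would score 0 at BL2 if the threshold applied at BL1 only. Table 6 ticks inclusion criteria at BL2 as well, and 9.2 names no visit. If the threshold also applies at BL2, a score below 3 there cannot occur.

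**Conclusion.** The point holds as a modest, no-cost improvement. Baseline PEG is undefined although two pre-randomisation readings are scheduled. If one reading is used, the treatment-effect variance is higher than it need be. Using both lowers it by about 2–4% at the plan's inputs, roughly one point of power, and by about 5–10% if the true correlation is 0.5–0.6, a value the documents do not give. The loss is conditional, because the plan does not say that only one reading will be used.

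It would be wrong to read this as regression to the mean entering the primary result. That analysis compares randomised arms with baseline as a covariate, and it is unbiased with either reading. Nor is the stated power undone by using one reading.

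The responder issue is secondary and conditional on entry being judged at BL1 only. In that case a BL1 baseline raises absolute 30% response by about 3–7 points over BL2 in both arms, under the assumed PEG distribution. That matters for published rates and for the cross-study comparison, not for the randomised contrast.

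**What to change.** In 15.4.2, define the baseline PEG adjustment as both the BL1 and BL2 scores, entered as two covariates or as their mean, in the primary and longitudinal PEG models.

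For the responder analyses:
- State which visit's PEG decides eligibility under 9.2, and reconcile 13.2.3 with the Table 6 tick at BL2.
- Prespecify the responder baseline. Report results against BL2 alongside the two-reading mean, noting that the mean reduces but does not remove regression to the mean.
- If a BL2 score of 0 turns out to be possible, say how it is handled.

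The cost is wording only. Both readings are already in Table 6 and precede randomisation. Section 6.1 requires an R33 protocol to be submitted to the funder before transition, which is a natural place for the change.
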